1.1 Abstract

Study Name: Predictive Role of Early Blood KLK10 and Other Neuroinflammatory Molecules on Clinical Outcomes of Acute Ischemic Stroke

Research Introduction: This study aims to investigate the dynamic changes and differential expression characteristics of neuroinflammatory molecules such as kallikrein-related peptidase 10 (KLK10), soluble triggering receptor expressed on myeloid cells 2 (sTREM2), and glial fibrillary acidic protein (GFAP) in the plasma of patients with first-ever anterior circulation acute ischemic stroke (AIS). It will analyze the correlation between these molecules and the severity of neurological deficits, infarct volume, brain edema, hemorrhagic transformation, progressive stroke, and clinical outcomes at three months. The goal is to assess the predictive value of these molecules for AIS prognosis, providing guidance for early treatment and new molecular targets for prevention and treatment.

Study Objectives :
1. To study the correlation between early plasma changes in neuroinflammatory molecules like KLK10 and clinical outcomes at three months post-AIS.
2. To investigate the relationship between early plasma changes in these molecules and hemorrhagic transformation post-AIS.
3. To explore the correlation between early plasma changes in these molecules and the occurrence of progressive stroke post-AIS.

Study subjects: 182 patients with first-ever anterior circulation AIS, regardless of gender and age, along with 91 age- and gender-matched healthy individuals as controls.

[figure not shown]
Research Site: Ruijin Hospital North Campus

Study Interventions : Non-interventional studies

Study duration: April 2024 - March 2025

Participant Duration: 3 months

1.2 Technology Roadmap

2. Study background

2.1 Research Significance

Stroke is the leading cause of death and disability in China. Intravenous thrombolysis or thrombectomy are currently the only approved early treatments for AIS (acute ischemic stroke). However, due to the limited time window, the number of patients benefiting from these treatments is restricted, leaving many patients with cerebral infarction. Studies have shown that neuroinflammatory molecules rapidly activate post-infarction and are involved in the pathogenesis of cerebral infarction. Moderate inflammation helps clear necrotic tissue and plays a crucial role in tissue repair and remodeling, while excessive inflammation can exacerbate ischemic neuronal damage and impair recovery (*Lancet Neurol*, 2019, 18(11): 1058-1066). Inflammatory markers in the blood rise quickly after 2 hours of stroke onset and continue to increase within 24 hours (*Stroke*.2022;53(7):2249-2259), making early detection of blood neuroinflammatory markers significant for predicting clinical outcomes in AIS. This study aims to dynamically measure changes in a set of neuroinflammatory molecules in the plasma, including KLK10, and analyze their correlation with the severity of acute neurological deficits, infarct volume, brain edema, hemorrhagic transformation, progressive stroke, and clinical outcomes at three months. Given the time-sensitive and challenging nature of AIS management, confirming that a set of neuroinflammatory molecules like KLK10 can accurately predict post-stroke clinical outcomes would have significant scientific value for guiding early treatment of AIS and could provide new molecular targets for stroke prevention and treatment.

2.2 Research Background

Microglia, the primary immune cells in the brain, are among the first cells to activate after AIS, playing a critical role in accelerating inflammation, increasing or reducing neuronal apoptosis, and regulating the post-stroke inflammatory microenvironment, thus affecting stroke prognosis (*J Neuroinflammation*. 2022;19(1):88). KLK10, also known as normal epithelial cell-specific molecule-1, is one of the 15 secreted serine proteases in the kallikrein family. Previous studies have shown that KLK10 is expressed in endothelial cells, where it participates in regulating endothelial inflammation and atherosclerosis (*Elife*. 2022;11:e72579). Our recent systematic observations of KLK10's spatial-temporal expression and cellular distribution in the brain after ischemia revealed that this molecule is expressed not only in cerebral endothelial cells but also in microglia and astrocytes. While it did not significantly increase in

the ischemic penumbra in the early stages (2-4 days post-ischemia), it was highly expressed in the infarct core area at 2 days post-ischemia and significantly co-labeled with microglia. The specific high expression of KLK10 in microglia in specific brain regions post-AIS suggests that it may be involved in early pathological damage after cerebral ischemia. Given that the permeability of the blood-brain barrier (BBB) changes within 6 hours of stroke onset (*Front Neurol.* 2020;11:594672), and since KLK10 is a secreted molecule, it is likely that its expression can be detected in the blood of AIS patients. Whether plasma KLK10 levels can reflect changes in neuroinflammatory damage in AIS patients and serve as a specific biomarker for predicting AIS prognosis remains unclear and warrants further investigation.

TREM2 is an innate immune receptor in the brain, consisting of an extracellular immunoglobulin-like domain, a transmembrane domain, and a cytoplasmic portion. Post-stroke, TREM2 is activated by nucleotides, lipid mediators, and other key factors released by apoptotic neurons, cells/myelin debris, playing an important role in regulating neuronal damage (*Front Immunol.* 2019, 10: 1668). Literature shows that TREM2 molecules are mainly expressed in microglia and can reflect their activation status. Elevated plasma sTREM2 levels are closely associated with increased risk of death and cardiovascular events one year after AIS onset (*J Neuroinflammation.* 2022;19(1):88).

Astrocytes, which also play a role in regulating brain inflammation, are the main glial cells in the central nervous system and are widely distributed throughout the brain. In their resting state, astrocytes provide structural and functional support to neurons, regulate synaptic activity by releasing gliotransmitters, and participate in synapse formation and remodeling (*Neurochem Int.* 2023;162:105456. *Neuroscience*, 2019, 396:73-78). After cerebral ischemia, astrocytes become activated and proliferate, limiting immune cell infiltration, repairing damaged BBB, and restoring stability in the brain's internal environment (*Front Immunol.* 2020, 11:1024. *Neurosci Lett*, 2019; 689: 45-55). Our studies and others have shown that astrocytes are extensively lost in the infarct core after cerebral ischemia, peaking at 48-98 hours post-stroke. The GFAP expressed by astrocytes can be released into peripheral blood, and its levels in the blood can reflect cell necrosis and BBB disruption (*Transl Stroke Res.* 2010;1(4):246-51) and can serve as molecular markers for distinguishing ischemic and hemorrhagic strokes (*Diagnostics (Basel).* 2023 Aug 25;13(17):2757).

The pathological damage mechanism of stroke is highly complex. Single neuroinflammatory molecules in plasma, whether sTREM2 or GFAP, are insufficient for predicting AIS prognosis. However, measuring a set of neuroinflammatory molecule levels may more accurately reflect the degree of neuropathological damage in AIS. Therefore, we propose that "early changes in plasma levels of KLK10, sTREM2, and GFAP, among other neuroinflammatory molecules, can effectively predict the clinical prognosis of AIS."

2.3 Expected Outcomes

To reveal whether early plasma levels of KLK10 and other neuroinflammatory molecules can serve as significant molecular markers for predicting the prognosis of AIS patients.

2.4 Risk/Benefit Assessment

2.4.1 Known Potential Risks

This study requires collecting 10ml of peripheral blood from AIS patients, with a total of three collections, and from healthy individuals, with a total of one collection. There is no significant potential risk to patients or healthy individuals, with the rare occurrence of fainting after blood draw.

2.4.2 Known Potential Benefits

The study does not provide significant benefits to patients, but the new findings from this study may help guide future treatment of stroke.

2.4.2 Potential Risk/Benefit Assessment

Given the rare occurrence of fainting in some patients after peripheral blood collection, symptomatic treatment will be administered. The success of this project has significant scientific value for guiding early treatment of AIS and providing new molecular targets for stroke prevention and treatment, potentially bringing important economic value.

3. Principal Investigator Information

3.2 Main Participants

Serial number	Name	gender	age	job title	Specialty	Whether GCP Training	Roles in the research (eg. PI, sub-I, CRC)
1	[name]	male	51	Chief Physician	Neurology	yes	PI
2	[name]	male	38	Deputy Chief Physician	Neurology	yes	sub-I
3	[name]	male	38	Indications Physician	Neurology	yes	sub-I
4	[name]	male	33	Indications Physician	Neurology	yes	CRC
5	[name]	female	29	Hospitalization Physician	Neurology	yes	CRC

4. Research Objectives

- 1) To determine whether early KLK10 and a group of neuroinflammatory molecules in plasma can serve as molecular markers for predicting clinical prognosis in AIS (Acute Ischemic Stroke).
- 2) To determine whether early KLK10 and a group of neuroinflammatory molecules in blood can serve as molecular markers for predicting hemorrhagic transformation in AIS.

5. Study Design

5.1 Overall Design

A total of 182 patients with first-ever anterior circulation AIS (Acute Ischemic Stroke) hospitalized in the Neurology Department at the Northern Campus of our hospital will be selected as the observation group, and 91 healthy individuals undergoing physical examination will be selected as the control group. For AIS patients, 10 ml of elbow venous blood will be collected at admission and then at 24 hours and 7 days after stroke onset. For healthy individuals, 10 ml of fasting elbow venous blood will

be collected once. The dynamic changes and differential expression characteristics of a group of neuroinflammatory molecules, including KLK10, sTREM2, and GFAP in plasma will be observed. The early changes (at admission and 24 hours after onset) of these neuroinflammatory molecules in plasma will be compared and analyzed in relation to the severity of acute neurological deficits (NIHSS score), infarct volume, brain edema, hemorrhagic transformation, occurrence of progressive stroke, and clinical prognosis at 3 months (mRS score), to evaluate the predictive value of these molecules for clinical outcomes after AIS.

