7.1.4 Items and frequency of clinical and laboratory examinations to be conducted

- 1) Collect reports of complete blood count and biochemical tests upon admission: including neutrophil and lymphocyte counts, blood glucose, creatinine, and high-sensitivity C-reactive protein levels.
- 2) Collect blood pressure information upon admission.
- 3) Collect reports of cranial MRI or CT scans upon admission, and record the Alberta Stroke Program Early CT Score (ASPECTS) (0-10 points).
- 4) Measure levels of neuroinflammatory markers KLK10, sTREM2, and GFAP in plasma at admission, and at 24 hours and 7 days after stroke
- 5) Assess the degree of neurological impairment using the National Institutes of Health Stroke Scale (NIHSS) at admission, and at 24 hours, 4 days, 7 days, and discharge after stroke.
- 6) Collect information on infarct volume within 7 days after stroke, measured using diffusion-weighted imaging (DWI) (J Neuroinflammation. 2020 Apr 7;17(1):107).
- 7) Collect information on brain edema grading within 7 days after stroke, measured using non-contrast cranial CT scans. The severity of brain edema in AIS patients is assessed with a score of 0-3 based on our established method (Clin Neurol Neurosurg. 2022 Nov 2;223:107507).
- 8) Collect information on hemorrhagic transformation within 7 days after stroke, measured using non-contrast cranial CT scans.
- 9) Record the Modified Rankin Scale (mRS) score at 3 months after stroke.

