7.6 Research Plan

Visit	Screening period	Observation period					Follow-up period
		1 day after onset	On admission	24 hours after onset	24 hours after onset	7 days after onset	
Informed consent	×						
Inclusion/Exclusion Criteria	×						
Basic information collection	×						
Peripheral venous blood collection		×		×	×	×	
NIHSS score		×		×	×	×	
blood sugar		×					
KLK10, sTREM2 and GFAP detection		×		×	×	×	
MRI						×	
CT	×					×	
mRS score							×

8. Discontinuation of study intervention and discontinuation/withdrawal of study subjects

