9.2 Secondary Endpoint Evaluation

- 1) Investigate the correlation between plasma KLK10, sTREM2, and GFAP levels and mortality at 3 months after stroke onset.
- 2) Examine the correlation between plasma KLK10, sTREM2, and GFAP levels and hemorrhagic transformation after infarction, based on brain CT scans to evaluate hemorrhagic transformation of cerebral infarction within 7 days after stroke onset.
- 3) Explore the association between plasma KLK10, sTREM2, and GFAP levels and the occurrence of progressive stroke, with neurological deficits assessed using the NIHSS score. Progressive stroke is diagnosed if the NIHSS score increases by 2 points within 7 days after stroke onset.

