10.3 Analysis of Secondary Study Endpoints

- 1) The correlation between plasma KLK10, sTREM2, and GFAP levels and hemorrhagic transformation and mortality at 3 months was investigated: univariate and multivariate logistic regression models were used to evaluate independent predictors, and ORs and 95% CIs were calculated. ROC curves were drawn and AUCs were calculated.
- 2) The association between plasma KLK10, sTREM2 and GFAP levels and the occurrence of progressive stroke was studied: univariate and multivariate logistic regression models were used to evaluate independent predictive factors, calculate OR and 95%CI. ROC curves were drawn and AUC was calculated.

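### For progressive stroke and hemorrhagic transformation, a 24-h marker level may be drawn after the event it is meant to predict, because the plan neither names the draw nor requires the event to follow it

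*Combined protocol and SAP*

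**What the plan says.** Section 5.1 schedules blood draws at admission, 24 h and 7 days after onset. It relates "The early changes (at admission and 24 hours after onset) of these neuroinflammatory molecules in plasma" to a list of outcomes that includes hemorrhagic transformation and progressive stroke, and gives the purpose as "to evaluate the predictive value of these molecules for clinical outcomes after AIS". The second objective in section 4 asks whether the markers "can serve as molecular markers for predicting hemorrhagic transformation in AIS".

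Both event windows in section 9.2 (secondary endpoints) run from onset with no lower limit. For progression: "Progressive stroke is diagnosed if the NIHSS score increases by 2 points within 7 days after stroke onset". For bleeding, CT is used to "evaluate hemorrhagic transformation of cerebral infarction within 7 days after stroke onset". Section 7.1.4 schedules the NIHSS "at admission, and at 24 hours, 4 days, 7 days, and discharge after stroke".

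Section 10.3 specifies univariate and multivariate logistic regression with ROC curves. For progression it reads "The association between plasma KLK10, sTREM2 and GFAP levels and the occurrence of progressive stroke was studied". It mentions no draw, no landmark time and no handling of events that came before the draw. Section 7.3, on reducing bias, is marked not applicable.

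**The concern.** A predictor has to be measured before the outcome. Admission can be at any time up to 24 h after onset (6.1), so the gap between admission and the 24-h draw can approach a full day. A 2-point NIHSS rise seen at the 24-h assessment already meets the progression definition. Intracranial hemorrhage is excluded under 6.2, but that is an entry criterion and does not cover bleeding after admission.

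If worsening or bleeding raises a marker, the 24-h level partly records the event. Section 2.2 makes this plausible for GFAP and bleeding: it describes blood GFAP as an indicator of necrosis and barrier damage that can separate hemorrhagic from ischemic stroke. The documents are silent on whether KLK10 or sTREM2 rises after progression or bleeding. What is at stake is the reading of the 24-h OR and AUC as early prediction.

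**Working it through.** **Order of draw and event, from the text**

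| Item | Time from onset | Source |
|---|---|---|
| Admission draw and NIHSS | 0-24 h | 5.1, 6.1, 7.1.4 |
| 24-h draw and NIHSS | 24 h | 5.1, 7.1.4 |
| Progression counted | up to day 7, no lower limit | 9.2 |
| Hemorrhagic transformation counted | up to day 7, no lower limit | 9.2 |

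The admission level precedes both events: progression is a rise after the first NIHSS, and hemorrhage is excluded at entry. The 24-h level has no such protection.

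**Size**

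The plan has no figure of its own on this point to reproduce. From the documents: 182 patients and two-sided 5% tests. Assumed: events in 10% or 25% of patients; a marker with no predictive value; a rise of d SD once an event has happened; a share s of events that precedes the 24-h draw.

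*What s would be at a constant event rate.* With arrival uniform over 0-24 h, the mean gap from admission to the draw is 12 h. The remaining window is 168 - 24 = 144 h. So s = 12/(12 + 144) = 7.7%, about 8%. A larger share needs a higher rate before the draw, by the ratio (s/12)/((1-s)/144): 5.1 at s = 30% and 28 at s = 70%.

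*Expected AUC* = 0.5 + s × (Φ(d/√2) - 0.5). For d = 0.5, Φ(0.354) = 0.638, so at s = 30% the AUC is 0.5 + 0.30 × 0.138 = 0.541. The true value is 0.50.

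*P<0.05 for the null marker*, by simulation of 182-patient studies with a two-sample t-test (ranges cover 10% and 25% events; repeat runs differ by about 1-2 points):

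| Early share s | Rise d | AUC | P<0.05 |
|---|---|---|---|
| 8% | 0.5 SD | 0.51 | about 6% |
| 30% | 0.25 SD | 0.52 | 7-8% |
| 30% | 0.5 SD | 0.54 | 10-14% |
| 30% | 1 SD | 0.58 | 23-40% |
| 70% | 0.5 SD | 0.60 | 29-51% |

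With early events excluded, the rate returns to about 5% in every row.

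**Cost of excluding early events (progression, 24-h level)**

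Expected events are 0.10 × 182 = 18.2 to 0.25 × 182 = 45.5. The loss is s times that: about 1.5-4 at 8%, 5-14 at 30% and 13-32 at 70%. For a true marker with an assumed OR of 2.0 per SD and 10% events, power falls from about 77% to about 72%, 65% and 32%. Repeat runs agree within about 3 points. These powers are without further covariates.

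**Adding the NIHSS change to 24 h as a covariate**

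A patient already at +1 by 24 h needs only one more point to count as progressed. Suppose 10-20% of patients are in that position, with 3-5 times the odds of later progression and a 0.25 SD marker rise. A null marker then reaches P<0.05 in 5-8% of studies in the restricted set, and in 4-5% with the covariate. At 10% events and s = 70% only 18.2 × 0.3 = 5.5 events remain. With the covariate, power there is about 27% and about 14% of fits fail or show separation.

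**The case against.** The strongest reply is that the effect may be negligible. At a constant event rate it is close to nil, and a material effect needs both clustering of events before the draw and a marker rise after the event. The documents establish neither. This stands as a limit on size. It does not remove the gap in the plan, because clustering is not ruled out either.

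Second, 10.3 names no draw, so the error occurs only if the 24-h level is used. That is correct, and the point is conditional for that reason. Section 5.1 does, however, list that level among those used to judge predictive value.

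Third, the wording is often softer than prediction: 9.2 and 10.3 mostly speak of association or correlation, and section 4 does not list progression. This also stands in part. For hemorrhagic transformation, section 4 states prediction outright; for progression, the predictive purpose comes from 5.1 and from the reference to predictive factors in 10.3.

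Several stronger readings are tempting and are not supported:

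- A reader might infer that the 24-h results will be false positives. Without event timing or marker response, the documents do not show that.
- A reader might infer that the CT schedule cannot date bleeding. The visit table in 7.6 appears to place CT at screening and "7 days after onset", but its columns are damaged, and 7.1.4 allows CT scans at any time within 7 days. Only that the scheduled scans may not date it is supportable.
- A reader might extend the point to the primary analysis. The 3-month mRS comes after the early draws and is not exposed in this way.
- A reader might add that variable time from onset to the admission draw biases the primary model. With OR 2.0 taken per SD, a marker rise of 0.5-1.7 SD over 24 h leaves an OR of 1.98-1.84, so this gives no reason to change that model.

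**Conclusion.** The point holds for two secondary endpoints and for the 24-h level only. Followed as written, the plan allows an event that precedes the draw to be scored as predicted by it, and nothing in 9.2 or 10.3 prevents this. The consequence ranges from almost none (AUC about 0.51, P<0.05 in about 6% at an 8% early share) through 10-14% at a 30% share to roughly 29-51% at 70%, all for a null marker with a 0.5 SD rise. Event frequency, early share and size of rise are assumptions, and the mechanism has documentary support only for GFAP and bleeding. It should be settled before analysis: a reported 24-h AUC could not otherwise be read as prediction, and choosing the draw after seeing results would add selection.

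**What to change.** In 10.3:

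1. State which draw each model uses, and name the admission level as the predictor for both endpoints. This keeps all events.
2. Progressive stroke: use the 24-h level only in patients who have not met the 9.2 definition by the 24-h NIHSS. State the admission NIHSS as the reference score (9.2 names none), so that the endpoint itself is unchanged. Add the admission-to-24-h NIHSS change as a covariate only if enough events remain, with the minimum number fixed in advance.
3. Hemorrhagic transformation: report the 24-h level as an association, not as prediction, unless an available CT shows that the bleeding came after the draw.

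This is a change of analysis wording. The admission and 24-h NIHSS are already collected, and no draw or scan is added. The price is the loss of early events, and hence of power, in the 24-h progression analysis. The loss is small when early events are few and large when they are many, which is also when the unrestricted analysis would mislead most.

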5.2 Defining study endpoints

The study is completed when patients have completed blood sample collection according to the study protocol and follow-up at 3 months after stroke onset. For healthy controls, the study is completed after the initial blood sampling and baseline investigation.

5.3 Determining sample size

Assuming a 40% probability of poor prognosis at 3 months after AIS, with an OR of 2.0 for high KLK10 expression and a correlation coefficient of 0.5 between KLK10 and other influencing factors, a significance level of 0.05, and a test power of 0.8, the required sample size is calculated using PASS11 software's Logistic Regression module. A total of 182 AIS cases are needed. Additionally, 91 age- and gender-matched individuals will be selected as healthy controls in a 2:1 ratio.

6. Research subjects

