8.3 Loss to follow-up

To reduce loss of follow-up and missing data, patients who were not followed up on time were contacted by telephone.

9. Study endpoint evaluation

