9.1 Primary Endpoint Evaluation

The study examines the association between plasma levels of KLK10, sTREM2, and GFAP with favorable functional outcomes at 3 months after stroke onset.

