10.1 General Methods

For descriptive statistical analysis, measurement data conforming to a normal distribution are expressed as mean \pm standard deviation; measurement data not conforming to a normal distribution are expressed as median (interquartile range); count data are expressed as rates or proportions. For comparing two groups of measurement data with normal distribution and equal variance, an independent two-sample t-test is used; for comparing two groups of measurement data not conforming to normal distribution and equal variance, a non-parametric Mann-Whitney U test is used. For count data in contingency tables, Pearson's chi-square test is used if conditions are met; otherwise, Pearson's chi-square test with continuity correction or Fisher's exact test is applied. All tests are two-tailed, with $P < 0.05$ considered statistically significant.

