10.2 Primary Endpoint Analysis

Investigate the association between plasma KLK10, sTREM2, and GFAP levels and functional prognosis at 3 months: Univariate and multivariate logistic regression models are used to evaluate independent predictors, and odds ratios (OR) with 95% confidence intervals (CI) are calculated. ROC curves are plotted and the area under the curve (AUC) is calculated.

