10.5 Baseline Descriptive Analysis

Descriptive statistics are used to compare demographic characteristics and laboratory indicators at baseline between groups. Continuous variables such as age, blood pressure, blood glucose levels, infarct volume, ASPECTS score, neurological function (NIHSS) score, and levels of neuroinflammatory molecules (KLK10, sTREM2, and GFAP) are expressed as mean (standard deviation) or median (interquartile range). Categorical variables such as the presence of hypertension, diabetes, hyperlipidemia, history of stroke, and occurrence of malignant brain edema are expressed as n (percentage). Fisher's exact test is used to assess differences in categorical variables, and the Kruskal-Wallis Rank Sum test is used to detect differences in continuous variables..

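### The inputs in section 5.3 do not give 182 patients at 80% power, and the unit of the odds ratio is not stated

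*Combined protocol and SAP*

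**What the plan says.** Section 5.3 holds the plan's only sample-size and power statement. Its inputs are:

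- outcome risk: "Assuming a 40% probability of poor prognosis at 3 months after AIS";
- effect and adjustment: "with an OR of 2.0 for high KLK10 expression and a correlation coefficient of 0.5 between KLK10 and other influencing factors";
- significance level 0.05 and power 0.8, run in the logistic-regression module of PASS11.

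The result is "A total of 182 AIS cases are needed". The 91 healthy controls are half of that number and do not enter a model of 3-month outcome.

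Section 5.3 does not give sidedness, but 10.1 does: "All tests are two-tailed". It names no formula, no unit for the OR, no cut-off for high KLK10, no expected share of patients above a cut-off, and no allowance for losses. On losses, 8.3 offers only telephone contact with patients who miss follow-up ("To reduce loss of follow-up and missing data").

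Elsewhere KLK10 is treated as a level. Section 9.1 reads "The study examines the association between plasma levels of KLK10, sTREM2, and GFAP with favorable functional outcomes at 3 months", and 10.2 reads "Investigate the association between plasma KLK10, sTREM2, and GFAP levels and functional prognosis at 3 months". Section 10.3 uses the same term for the secondary endpoints, and 10.5 lists the three molecules among its continuous variables. Section 10.2 plans odds ratios but gives no unit or scale for them.

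**The concern.** The inputs are specific enough to put into the usual formula, and the result is not 182. At least one reported input, or the reported power, therefore differs from what was run.

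The missing unit matters more than the arithmetic. The same sentence can describe a study with ample power or one that would miss its own target effect about half the time. The wording in 5.3 suggests a contrast between high and low KLK10, while the analysis sections point to a continuous level. Until the unit is stated, a reader cannot say what a null primary result would mean.

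**Working it through.** **Inputs.** P = 0.40, OR = 2.0 (ln 2 = 0.6931), 0.5 for the association of KLK10 with other factors, alpha 0.05, power 0.80 (all from 5.3); two-sided (10.1). The value 0.5 is tried as a correlation (R-squared 0.25) and as R-squared 0.5.

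**1. Trying to reproduce 182, OR per 1 SD (Hsieh-Block-Larsen formula, continuous covariate).**

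N = (z_alpha/2 + z_beta)² / [P(1−P)(ln OR)²] / (1−R²)

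- Unadjusted: (1.960 + 0.8416)² / (0.24 × 0.6931²) = 68.07
- R² = 0.25: 68.07 / 0.75 = 90.76, so 91
- R² = 0.50: 68.07 / 0.50 = 136.14, so 137

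One-sided, the two adjusted results are 72 and 108. An older version of the formula gives 131 and 196 two-sided. None is 182. To reach 182 at 80% power, R² would have to be 1 − 68.07/182 = 0.626.

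**2. Formula power at 182, OR per 1 SD.** Power = Φ(√[182(1−R²)(0.24)] × 0.6931 − 1.960)

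- R² = 0.25: Φ(5.724 × 0.6931 − 1.960) = Φ(2.007) = 97.8%
- R² = 0.50: Φ(4.673 × 0.6931 − 1.960) = Φ(1.279) = 90.0%

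**3. Where 182 might come from.**

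- Power 0.90 in the formula of step 1: (1.960 + 1.2816)² / (0.24 × 0.6931²) = 91.12, and 91.12 / 0.50 = 182.25 (183 if rounded up).
- Doubling the 91 from step 1: 2 × 91 = 182.
- Inflating 136.14 for a 25% loss: 136.14 / 0.75 = 181.5.

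The documents state none of these.

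**4. OR for high versus low KLK10.** The share that is high, B, is not given; 0.50 is assumed. Taking 40% as the risk in the low group, p0 = 0.400 and p1 = 0.571 (mean 0.486).

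N = [z_alpha/2 √(p̄(1−p̄)/B) + z_beta √(p0(1−p0) + p1(1−p1)(1−B)/B)]² / [(p1−p0)²(1−B)] / (1−R²)

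- Unadjusted: (1.385 + 0.586)² / (0.1714² × 0.5) = 264.5
- R² = 0.25: 352.7, so 353. R² = 0.50: 529.0
- Power at 182: 51.8% or 37.1%

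Taking 40% as the overall risk instead (p0 = 0.318, p1 = 0.482), N is 368.1 or 552.1, and power at 182 is 50.1% or 35.8%. With an assumed 25% high, the need rises to about 467 or 700 with 40% in the low group.

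**5. Simulation of the per-SD reading.** Settings: 8,000 runs each, one normal covariate correlated with KLK10, overall 40% poor outcome, adjusted Wald test. The covariate's own effect on outcome is an assumption, because 5.3 gives none.

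| N = 182 | R² = 0.25 | R² = 0.50 |
|---|---|---|
| Covariate has no effect on outcome | 96.1% | 86.0% |
| Covariate OR 2.0 per SD | 92.8% | 78.8% |

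At the formula's own sizes, with no covariate effect, simulated power is 72.7% (N = 91) and 74.0% (N = 137), so the formula is optimistic here.

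**6. Losses.** If 10% or 20% were not analysed (an assumption; 164 or 146 patients), simulated power with a covariate that has no effect is about 94% or 91% at R² = 0.25, and about 82% or 77% at R² = 0.50. It would be lower with a prognostic covariate.

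**The case against.** The strongest reply is that this is a reporting slip. Changing the power from 0.8 to 0.90 and reading 0.5 as R-squared brings the formula to 182.25, which points to a continuous KLK10 and a sample size that is conservative by formula. The analysis sections favour the continuous reading too. That is a plausible account, and it is the reason to look at the PASS output first. It remains an inference: two other routes also land near 182, and the text calls 0.5 a correlation coefficient, which literally means r.

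Three stronger readings are tempting, and the documents support none of them.

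- *The study is underpowered.* A reader might infer this from the wording about high expression. It rests on a high/low cut for which the documents give neither a cut-off nor a share, and 9.1, 10.2, 10.3 and 10.5 speak of levels or continuous variables.
- *The true power is safely above 80%.* A reader might infer this from the 98% and 90% in the formula. If the other influencing factors in 5.3 are prognostic, as the phrase suggests, power at R-squared 0.5 can fall to about 79% even with all 182 analysed. Losses lower it further. So may 7.4, where an mRS of 3 is neither a good nor a poor outcome.
- *80% at 182 is right after all.* The 79% in simulation is close to 80%, but it needs a covariate effect that 5.3 does not contain and that the formula does not use. It does not restore the stated derivation.

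**Conclusion.** The point holds, with high confidence on the mismatch: by the standard formula, the stated inputs at two-sided 0.05 and 80% power give 91 or 137 with the OR per SD, and about 353 or more for a high/low OR at an assumed even split. They do not give 182.

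What 182 delivers depends on facts that are not stated. With the OR per SD, it is about 98% or 90% by formula, and between about 96% and 79% in the simulated settings, according to R-squared and the assumed covariate effect. With a high/low OR at 50:50, it is about 50% or less. The continuous reading fits the analysis sections better, so the likelier outcome is a misdescribed calculation rather than a sample that is too small. This is a correction worth making before analysis, not a reason to enlarge the study.

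**What to change.** 1. Check the PASS output behind 182, and correct 5.3 so that the inputs, the power and the N agree.
2. In 5.3, state the power actually used, whether 0.5 is r or R-squared, the formula, and the unit of the OR.
3. Make that unit match the KLK10 term in the 10.2 model. Since 10.2 analyses levels, this could be per 1 SD on a named scale (raw or log).
4. Restate the power by the named formula at 182 and at the number expected to be analysed after losses. Say that it is approximate and falls if the covariates are prognostic. The simulated figures above depend on an assumed covariate effect and should not be copied into 5.3 without it.
5. If a high/low cut is kept, state the cut-off and the expected share of patients above it, and restate the power or the detectable OR.

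The cost is one paragraph in 5.3 and one sentence in 10.2, with no added patients. The only downside is that the stated power may change, and it would be lower if a high/low cut is kept.
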